## Data Analyses

Aims 1 & 2. Conduct user-centered design of passive mobile self-tracking to support Veterans' management of their mental health. Study the feasibility, acceptability and safety of passive self-tracking of mental health that includes feedback of mental health status to the Veteran.

Before deployment of the app, user-centered design is conducted to inform further development of the app and intervention. Using ATLAS.ti, transcripts of clinician interviews, patient focus groups, and notes from in-lab patient usability testing will be coded deductively for major subthemes regarding usefulness, ease of use, attitudes and behavioral intention towards use, acceptability, strengths and weaknesses, barriers and facilitators of use, safety, and recommendations about revisions and implementation efforts. Results inform modifications of the app, and refinement of methods for enrollment and maintenance of participation.

During deployment of the app, formative evaluation is conducted to understand and strengthen development, deployment and future implementation. Feasibility is characterized by studying the extent to which potential subjects enroll, maintain involvement and complete study assessments. Acceptability is characterized by counting days during which patients use mobile sensing and dashboards, and by analyzing data from semi-structured interviews. Safety is measured using the rate of serious adverse events. The following may be considered serious adverse events: death, life-threatening experience, inpatient hospitalization, persistent or significant disability, or incapacity. Important medical events that do not result in death or require hospitalization may be considered serious adverse events if they jeopardize the participant or require medical or surgical intervention to prevent one of the outcomes above.

Using multivariate analyses, we study whether quantitative baseline patient characteristics described above are associated with feasibility, acceptability, and safety. Qualitative data from patients 3-month and 9-month interviews are used to evaluate themes related to the feasibility, acceptability and safety of sensing. Qualitative data from post-intervention clinician interviews are used to evaluate themes related to patient engagement, findings, implementation, and resources for sustainability and incorporation into routine practice. Using ATLAS.ti, transcripts of interviews will be coded deductively for major subthemes regarding acceptability, strengths and weaknesses, barriers and facilitators of use, safety, and recommendations about future revisions and implementation efforts. The qualitative findings will be triangulated with findings from the other measure of acceptability and safety to examine whether concordance exists among these measures of the intervention. Should analytic anomalies in the quantitative findings arise, the qualitative data will be explored to illuminate possible explanations for unexpected findings. At 3 and 9 months, 26 individuals should be sufficient to provide data saturation regarding acceptability of the intervention using qualitative data.

Aims 3 & 4. Use mobile sensor and phone utilization data to develop individualized estimates of sociability, activities, and sleep as measured by weekly interview. Study the predictive value of using data on sociability, activities, and sleep to identify exacerbations of psychiatric symptoms.

We study digital phenotypes that are informative as predictors of behaviors and symptoms. These include both short- and long-term behavioral data, i.e. what an individual has done recently and how their behavior and symptoms have changed over time. There will be multiple real time data streams collected that will be continuous and intermittent sequence activities to assess behaviors (Table 1). Even though the data can be represented as a function of time  $t$ , they are being collected at vastly different frequencies and durations, and with different noise and error rates. Thus, we use a two-phase analytics pipeline of modeling. In phase 1, we conduct data preprocessing that derives features capturing events from the data collected. In phase 2, we conduct predictive analytics using machine learning that models correlations between sensor and phone utilization data, and behavioral assessments and symptoms.

From the project's mobile app, we obtain highly detailed patient level information over a 9 month follow up period and transmit it to the server database. In the data preprocessing phase, we reduce these mobile data to continuous summaries that retain more information than categorical ones. Sensor and utilization data are captured at varying frequencies for the different domains. For measures that are updated in seconds and minutes, we summarize data using activity profiles (over a day or a week), defined as the amount of time the person spends at an activity level (e.g., above a certain threshold) or engaged in an activity (e.g., walking, exercising, riding in a motor vehicle). Movement measured through the accelerometer will be transformed to an activity profile by defining activities from no movement to faster movement (using thresholds). Light and sound levels will be thresholded from low to high and the amount of time spent at each level captured. In this way, problems with temporal alignment of data are mitigated, transforming data into densely measured functional data, conceptualized as longitudinal functional data. Here the profile constitutes the functional observation varying over levels (summarizing over a day or a week) and days/weeks constitute the longitudinal repetitions. For measurements summarized over days (e.g., total phone calls, total hours of sleep), data are conceptualized as longitudinal data. We also include static patient measures from baseline that could improve the accuracy of models, such as demographics, prior medication adherence, housing status, psychiatric symptoms, cognitive deficits associated with SMI, and social and occupational functioning.

For data obtained from smartphones, an issue that will arise frequently is missing data. When adjusting for missing data in creating activity profiles, we will consider various approaches. One approach is a similarity assumption which states that the proportion of time that a participant spends at a given activity level during the observed times is similar to the proportion in the unobserved times. This is similar to a missing at random assumption in longitudinal data analysis. For example, time spent at different

activity levels (activity profile) could be rescaled to include time over unobserved periods as well. Another approach is to use the planned machine learning approaches to also evaluate missing data patterns.

In Aim 3 we develop individualized estimates of sociability, activities and sleep. We will aggregate daily mobile data on a weekly basis to predict behavioral measures that are also obtained weekly. Summary statistics such as mean, variance, min, or max will be used for aggregation as deemed appropriate. We will then employ various machine learning algorithms to build, train, and select prediction models for each of the patient behavioral assessment domains using features of sensor and phone utilization data (Table 1). Model development will proceed in three stages. First, we will utilize methods of unsupervised learning to cluster sensor and phone utilization data and extract features to reduce the dimensionality. Second, we will explore a number of supervised learning procedures to build candidate prediction models for patient behavioral assessments. Finally, we will use cross-validation to estimate the out-of-sample performance of the prediction models, and to select best model(s) from among the candidates.

To reduce the number of features upon which to build the prediction models, while preserving the maximum amount of information, the first strategy is to use principal component analysis (PCA). PCA reduces the dimensionality of a data set by identifying linear combinations of the features, the principal components, which maximize variability while remaining mutually uncorrelated. Building the models using fewer candidate features reduces the risk of overfitting, and using the principal components in place of the original features prevents problems of multicollinearity. The second dimension reduction strategy is to use FDR (false discovery rate) threshold. FDR-based thresholding gives an optimal way of adapting to unknown sparsity (only a small number of effects are significantly large) and may be viewed as an estimation procedure with an appropriate penalization scheme accounting for the number of selected variables.

Given the reduced number of features, various supervised machine learning algorithms will be used to train prediction models for patient behaviors and symptoms. At the preliminary analysis stage, a set of supervised learning algorithms will be explored to evaluate cross-sectional associations between mobile data features and patient behavioral assessments, with the goal of narrowing down the pool of candidate predictors. First, we will consider random forests. A random forest is a collection of decision trees, each built using a random sample of features, and trained on a bootstrap sample from the original data. Random forests are useful for identifying complex interactions among features due to the use of decision tree learning, while protecting against overfitting by means of bootstrap aggregation. Second, we will consider support vector machines (SVM). SVM is a method of supervised learning which classifies instances into categories by estimating a hyperplane that separates instances belonging to different classes. SVM may be used if the outcomes of interest, behaviors and symptoms, can be meaningfully categorized (e.g., high vs. low). Selected predictors from these approaches will be used in the next step of the model building process that takes into account the temporal correlation and time series nature of mobile data and patient assessments. We will use hidden Markov models to predict patients' current behaviors and symptoms based on current features and past patients' behaviors and symptoms. We view patients' features as observed states, and patients' behaviors and symptoms are hidden states that enjoy the Markov property. We will also use linear or generalized linear mixed effects models to predict patient behavioral assessments using selected features from the preliminary stage, while taking into account within-patient correlation in repeated measurements over time.

Models developed using supervised machine learning methods will be evaluated in terms of out-of-sample predictive performance using leave-one-out cross-validation (LOOCV). For time series modeling, models will be trained on times 1, ..., t-1, and evaluated on time t, for each time t. For cross-sectional modeling, models will be trained on all but patient i, and evaluated on patient i, for each patient i. Performance will be averaged across hold-out times/patients to obtain a LOOCV estimate of

generalization error. Quadratic loss will be used to evaluate prediction error. The selected model will be the one that minimizes LOOCV mean squared error.

In Aim 4, outcome data are collected weekly for each patient on three scales (psychosis, mania, depression). These scales each have a range of 1 to 7. The primary outcome will be the scale indicating the most severe symptoms in a 2-month window. We will evaluate the association between mobile data features identified in Aim 3 with this primary outcome using a mixed effects model to accommodate within patient data correlation due to repeated measures. Specifically, we will consider feature data from fixed time windows preceding the most severe symptoms. The outcome data distribution will be examined prior to model fitting, and an appropriate link function will be used in the mixed effects model.

Sample size and power considerations: In Aim 3, we extract features of mobile sensor and phone utilization data to estimate behaviors in the domains of sociability, activity, and sleep. The selected features should have a high correlation with behaviors to be a good estimate. Of 100 participants enrolled, assuming 30% attrition, we expect to have complete data on 70 participants (and substantial longitudinal data for a larger group). This sample size will provide over 95% power to detect a correlation of at least 0.50 at the significance level 0.05 using a two-sided test. In Aim 4, our inclusion criteria select for greater than average symptom risk, so we anticipate substantial symptoms. Previous research on 21 patients with SMI for a median of 134 days found that sensing data predicted symptom indicator scores with correlations in the range of 0.5 to 0.8. Given possible confounders, and since our sample may be more heterogeneous than prior research, the correlation in our study is anticipated to be lower than what was reported previously. With 100 enrolled, and assuming 30% attrition, we will have over 85% power to detect correlations of at least 0.35 between predictors of interest and symptoms assessments at the significance level of 0.05 using a two-sided test.

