### Patient Participant Assessments and App Download

For participants in the mobile sensing trial, after the informed consent process, research staff administer the baseline research assessment. Then the project app is downloaded to the participant's

phone. It is activated by staff using a code. Each time the app is activated on a device, a unique ID is created by the server. This ID connects data from the app with patient identifiers kept on the secure server. After the app is activated, it runs in the background and collects data passively with no further action from the user.

Participants will receive phone calls from study staff on a weekly basis throughout a 9-month study period to complete assessments by phone. Based on our experience with these assessment instruments, as staff get to know individual patients the time required for assessments becomes relatively brief. A semi-structured qualitative interview will also be conducted at 3 months by phone with a subsample of participants until data saturation is achieved. At the conclusion of the 9 month study period, the participants meet with research staff for a final follow-up interview. At this point, the project app will be deleted from the phone, and the participant will be notified that it is no longer functional. The final assessment will also include a qualitative component for a subsample of participants until data saturation is achieved.

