Sleep measures will focus on regular, uninterrupted sleep, in sufficient quantities represents one of key measures of mental health. Sleep measures collect data on ambient light, ambient sound, phone movement, lack of communication, and lack of use of the phone. Specific measures of Sleep we will attempt to gather:

- Quality: Is the individual having uninterrupted sleep
- Duration: what is the length of sleep the individual is having

Table 1. Data for Modeling of Behavioral Domains

Behavioral Domain	Input Data from Phone	Model Output Classifiers
Activities physical activity intensity and duration (walking, running, climbing stairs, riding bicycle) vs. sedentary organized activities: number and duration outside the individual's residence regular structured activities throughout each day (location and duration)	
 
• accelerometer sensor: acceleration force data for three coordinate axes
 
• linear accelerometer Android software: acceleration force data for three coordinate axes (excludes gravity)
 
• gyroscope sensor: rotation data for three coordinate axes
 
• rotational vector Android software: rotation vectors for three coordinate axes and scalar
 
• step counter Android software
 
• significant motion Android software: motion leading to change in location
 
• Activity Recognition Google API: still, on foot, on a bicycle, in a vehicle
 
• Fused Location Google API (uses GPS & wifi): location after 5 meters of movement
 
	
 
• Short International Physical Activity Questionnaire (4 items)
 
• Independence, Performance and Prosocial domains of the Social Functioning Scale (15 items)
 

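### The activity profile treats phone movement as the person's movement, with no step to separate a still person from a phone that is not being carried

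*Combined protocol and SAP*

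**What the plan says.** In the preprocessing text of Data Analyses (Aims 3 and 4), an activity profile is "defined as the amount of time the person spends at an activity level" or engaged in an activity. For movement the rule is: "Movement measured through the accelerometer will be transformed to an activity profile by defining activities from no movement to faster movement (using thresholds").

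The same section offers two approaches to missing data. The first is a similarity assumption: a person's share of time at each level "during the observed times is similar to the proportion in the unobserved times", with rescaling as the example. The second reads: "Another approach is to use the planned machine learning approaches to also evaluate missing data patterns". Observed time is not defined.

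Under Patient Participant Assessments and App Download, once activated the app is such that "it runs in the background and collects data passively with no further action from the user". The one stated coverage measure, under Formative evaluation assessments, is a monthly count of days on which the app recorded and transmitted.

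For sleep, Data Collected from Mobile Application says: "Sleep measures collect data on ambient light, ambient sound, phone movement, lack of communication, and lack of use of the phone". Table 1 adds location, screen and unlock events, call and message logs, and app use. It lists unlock and screen events under Sleep and not under Activities.

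**The concern.** The sensors describe the phone, while the profile is defined for the person. A phone that is charging, on a desk or left at home records no acceleration, no steps and no change of place whatever its owner is doing. Under the stated rule that time goes into the no-movement level.

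The other Activity inputs in Table 1 (gyroscope, step counter, significant motion, activity recognition, location) err in the same direction when the phone is left behind, so they cannot correct one another. The coverage count does not help either, because a switched-on phone on a table meets it.

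The plan reads little exercise and little movement outside the home as possible signs of mental health problems, and an uncarried phone produces exactly those readings. Features selected in Aim 3 go on to Aim 4, and participants see scores for these domains on a 1-100 dashboard. If carrying differs between people or changes from week to week, the features partly measure phone habits. If it also changes with symptoms, the result is bias as well as noise. The documents do not indicate its direction.

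**Working it through.** **1. The plan's own figures.** From Sample size and power considerations: 100 enrolled, 30% attrition, so n = 100 × (1 − 0.30) = 70; two-sided alpha 0.05; r = 0.50 (Aim 3) and r = 0.35 (Aim 4). Fisher z: power = Φ(atanh(r) × √(n − 3) − 1.96), with √67 = 8.185.
- r = 0.50: Φ(0.549 × 8.185 − 1.96) = 99.4%. The plan says over 95%.
- r = 0.35: Φ(0.365 × 8.185 − 1.96) = 84.9%, or 85.3% with a t-based critical value and bias term. The plan says over 85%.

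Both reproduce.

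**2. Effect on the level (illustration).** Assume a person is truly active 25% of the time, and the phone is left behind for a share u of the time, independently of activity. Recorded active share = 0.25 × (1 − u).
- u = 0.10: 22.5%
- u = 0.20: 20%
- u = 0.40: 15%

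If all of this time counts as observed, rescaling for missing data changes nothing. A constant understatement of this kind would not by itself alter a correlation. What matters is variation in carrying.

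**3. Effect of varying carry (illustration).** Let T be true weekly active time with coefficient of variation v, assumed 0.3 to 0.5. Let C be the carried share, independent of T, with coefficient of variation c = SD/mean. Recorded time is T × C. Then

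corr(T, TC) = v / √[(1 + v²)(1 + c²) − 1].

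Worked case, mean carry 0.6, SD 0.20, v = 0.3: c = 0.333; (1.09 × 1.111) − 1 = 0.211; √0.211 = 0.459; 0.3/0.459 = 0.653; 0.50 × 0.653 = 0.33.

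| Mean carry (SD) | r 0.50 becomes | Power, n = 70 | r 0.35 becomes | Power, n = 70 |
|---|---|---|---|---|
| 0.9 (0.05) | 0.49-0.50 | 99% | 0.34-0.35 | 83-84% |
| 0.8 (0.10) | 0.46-0.48 | 98-99% | 0.32-0.34 | 78-82% |
| 0.6 (0.20) | 0.33-0.40 | 79-94% | 0.23-0.28 | 48-66% |
| 0.5 (0.25) | 0.25-0.33 | 55-81% | 0.17-0.23 | 30-49% |

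Every carry mean, SD and v here is an assumption. The model has one feature, and it does not separate carry that varies between people from carry that varies between weeks.

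**4. Check on a tempting remedy.** Suppose all idle time is recoded as unobserved and the profile rescaled. For a person truly active 15% of the time, with 40% of time flagged although the person really was still, the rescaled share is 0.15 / (1 − 0.40) = 25%. Real inactivity is erased, and most strongly in the least active people.

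**The case against.** **The models are trained, not taken at face value.** The plan acknowledges differing noise and error rates, fits features to weekly interviews, treats behaviors as hidden states and selects by out-of-sample error. This stands in part. Training absorbs a constant understatement, and within-patient modeling can absorb some of a stable personal habit. It cannot remove carry that varies from week to week when no carry-related feature is offered to it.

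**The text is an outline.** Observed time is undefined, various missing-data approaches are to be considered, and nothing forbids treating uncarried time separately. So it is an inference that such time counts as observed, though the natural one because the app is recording. The movement rule, followed as written, still merges the two states.

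**The attenuation double-counts.** The plan sets 0.50 for the selected mobile features against behaviors, so device noise may already be inside it. The plan also combines many features where the illustration has one. Both points stand, which is why the table shows sensitivity only.

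**Stronger readings that the documents do not support.**
- A reader might infer that an idle phone is scored as sleep. Stillness and non-use are Sleep inputs, but so are ambient light, ambient sound and others. A phone in a lit or noisy room need not look like sleep, while one in a dark, quiet room might. This is a risk only.
- A reader might infer that Table 1 holds nothing that could detect an idle phone. It does hold such signals; the plan does not assign them to this use.

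**Conclusion.** The gap holds for the activity profile. Phone stillness is read as the person's stillness, nothing in the preprocessing separates the two, and the missing-data approaches do not reach time when the phone is on but elsewhere. The consequence is noise, and possibly bias, in the Aim 3 activity features and in what Aim 4 inherits from them.

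The size cannot be fixed from the documents. Under the assumed carry distributions the loss is negligible at a mean carry of 0.9 or more and substantial at 0.6 or less. As planned, the study would not show where in that range it lies.

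A reader might conclude that the stated power is wrong. It is not shown to be: both figures reproduce, and the attenuated values rest on assumed carry rates, a single feature and a 0.50 that the plan sets for measured features.

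**What to change.** Before applying the movement thresholds in Data Analyses:

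1. Use accelerometer, gyroscope, step and unlock/screen signals, all already in Table 1, to flag blocks with no motion, no steps and no phone use.
2. Keep these blocks as a separate phone-idle level instead of merging them into no movement.
3. Add the weekly phone-idle share as a candidate feature in Aims 3 and 4.
4. As sensitivity analyses, repeat the Aim 3 results (a) without weeks of high daytime idle share, with the cut-off set in advance, and (b) with idle blocks treated as unobserved and rescaled.

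The cost is some preprocessing code and a few sentences in the plan, with no added participant burden or data collection. The limitation is that idle blocks will include some truly motionless time, such as daytime sleep or withdrawal, which the study wants to detect. For that reason recoding them as unobserved belongs in a sensitivity analysis and not in the main one.

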#### *Data Collected from Mobile Application*

The app collects passive behavioral data for assessment in three domains that have previously been proven to be measurable using these data: sociability, activities, and sleep. Sensor data collected from the app is encrypted and cached locally on the device, securely transmitted to the platform's remote server when a data connection is available. Analyses will seek to correlate behavioral patterns with emotional well-being. Analyses will also conduct time-series analysis to monitor shifts over time. We

anticipate detecting acute health stress through shifts in behavior patterns. The app will passively collect behavior data in three domains: sociability, activity, and sleep.

Participants will be able to view the tracking of their activities, sociability and sleep over time, similar to how people currently view their step counts in mobile health app dashboards. Each of the behavioral domains in this project will be presented on a 1-100 scale, as numbers graphed over time.

Sociability explores social characteristics of the individual. Dynamic and active social lives are correlates of mental health. Concurrently, sudden changes in sociability, particularly a notable increase in introversion and isolation could be indicators of diminishing mental health. Sociability assesses social characteristics by collecting information on calls and texts made with the phone (the content of these communications is not assessed or recorded) and public interaction by measuring ambient sound in social environments. Specific measures of Sociability we will attempt to gather:

- Communication: regular communication with a diverse set of individuals by phone call, text messaging, or use of messaging apps
- Public Interaction: regular communication with others in person or spending time in a social environment

Activity measures an individual's day-to-day routine by monitoring activity, movement, location, and habits. Adhering to regular routines, engaging in exercise, and productive activity outside the home are indicators of mental health. Changes in routines, lack of exercise, and limited intentional movement outside the home can be signs of mental health issues. Specific measures of Activity we will gather:

- Routine: a regular and structured daily and weekly routine
- Exercise: regular exercise
- Activities: Engagement in activities, particularly outside of the individual's residence

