Sleep total sleep duration uninterrupted sleep regular daily sleep and wake times	Sleep: 
 
ambient light sensor: indoors, outdoors or dark location
 
ambient sound sensor: volume
 
significant motion Android software: motion leading to change in location
 
Fused Location Google API (uses GPS & wifi): location after 5 meters of movement
 
phone unlock, screen interactions and on-time duration
 
log of phone calls placed
 
log of messages sent
 
apps opened
 
app duration of use
 
	
 
Pittsburgh Sleep Quality Index Components 1, 2, 3, 6 (5 items)
 
Insomnia Problem items from the Insomnia Severity Index (3 items)
 

Sociability communication in person or in a public social environment communication with a diverse set of individuals communication with repeated partners	
 
log of phone calls placed with phone numbers
 
log of phone calls received with phone numbers
 
log of messages sent with phone numbers
 
log of messages received with phone numbers
 
social media apps opened
 
social media apps: keystrokes and duration used
 
messaging or email apps opened
 
messaging or email apps: keystrokes and duration used
 
ambient sound sensor: volume
 
Activity Recognition Google API: still, on foot
 
Fused Location Google API (by GPS & wifi): location after 5 meters of movement
 
	
 
Objective Frequency of Social Contact scale (6 items)
 
Abbreviated Lubben Social Network Scale (6 items)
 

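### The level profiles planned for light, sound and movement discard clock time and order within the day, and no other feature is specified for sleep continuity, sleep timing or routine

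*Combined protocol and SAP*

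**What the plan says.** The data preprocessing text in Data Analyses (Aims 3 & 4) gives a general rule: "For measures that are updated in seconds and minutes, we summarize data using activity profiles (over a day or a week". A profile is defined there as an amount of time at a level or in an activity. The rule is then applied by name to two groups of streams. For movement: "Movement measured through the accelerometer will be transformed to an activity profile by defining activities from no movement to faster movement (using thresholds". For light and sound: "Light and sound levels will be thresholded from low to high and the amount of time spent at each level captured". The axis of the profile is also fixed: "Here the profile constitutes the functional observation varying over levels (summarizing over a day or a week". Days or weeks are the only repetitions. The Aim 3 text then aggregates daily data to the week: "Summary statistics such as mean, variance, min, or max will be used for aggregation as deemed appropriate".

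The content that these features should represent is set out under Data Collected from Mobile Application. The Sleep row of Table 1 reads "total sleep duration uninterrupted sleep regular daily sleep and wake times". The Activities row includes "regular structured activities throughout each day (location and duration". The text before the table lists "Routine: a regular and structured daily and weekly routine" among the activity measures, and gives uninterrupted sleep as the meaning of sleep quality.

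**The concern.** Total duration of sleep and amounts of activity are functions of time at each level. Continuity of sleep, the times of falling asleep and waking, and the structure of a day are not. They depend on which minute follows which, and on the clock. A profile indexed by level, with the day or week as its only time index, keeps neither. The loss would occur in a fully observed record, so the planned rescaling for unobserved time does not address it.

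Two things are at stake. If the Aim 3 sleep or activity model performs poorly, the study could not tell whether phones fail to capture these behaviours or the summary rule removed the information. Aim 4 takes its predictors from the features identified in Aim 3, so it would inherit the same gap. The hidden Markov and mixed models work on the reduced features and cannot restore order lost before they are fitted.

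**Working it through.** The plan gives no figure on this point, so there is none to reproduce. All numerical inputs below are assumptions made for illustration, except the planned summaries themselves.

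**1. Does the profile determine continuity and timing?** Take one binary state (dark, quiet and still, or not), 1,440 minutes a day, 7 days, nothing missing.

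- Week A: one 480-minute block starting at minute 60 every day.
- Week B: eight 60-minute blocks with 20-minute gaps (8 × 60 = 480), the first starting at minute 0, 300, 600, 120, 480, 720 and 240 on successive days.
- Regularity index: 200 × (share of minutes in the same state 24 hours later) − 100.

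| Quantity | Week A | Week B |
|---|---|---|
| Minutes at the low level, each day | 480 | 480 |
| Weekly mean / variance / min / max | 480 / 0 / 480 / 480 | 480 / 0 / 480 / 480 |
| Bouts per day | 1 | 8 |
| Longest bout (min) | 480 | 60 |
| Onset (minute of day) | always 60 | 0 to 720 |
| Regularity index | 100 | 13 |

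The planned summaries are identical; continuity, timing and regularity are not. This step needs no distributional assumption.

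**2. How much does a total say about awakenings?** Let sleep duration D have SD 60 min, let the number of awakenings A be Poisson with mean 2 and independent of D, and let each awakening last d minutes. Quiet time is Q = D − dA. Then

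R² = Cov(Q, A)² / [Var(A) Var(Q)] = (2d)² / [2(3600 + 2d²)] = 2d² / (3600 + 2d²).

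- d = 5: 50/3650 = 1.4%
- d = 10: 200/3800 = 5.3%
- d = 20: 800/4400 = 18.2%

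**3. How much do daily totals say about irregular onset?** Let a person's true onset SD, σ, be uniform on 10 to 120 min, with seven normally distributed onsets a week.

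Benchmark, using the SD of the seven onset times: Var(σ) = 110²/12 = 1008.3; E(σ²) = 65² + 1008.3 = 5233.3; the expected sample SD is 0.9594σ for seven values. So R² = 0.9594² × 1008.3 / [0.9594² × 1008.3 + (1 − 0.9594²) × 5233.3] = 928.1 / (928.1 + 416.6) = 69.0%.

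Planned summaries: let daily duration be a constant − c × (onset delay) + noise, and regress σ on the weekly mean, SD, min and max of the daily totals (200,000 simulated person-weeks).

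| Coupling c | Noise SD (min) | R² |
|---|---|---|
| 0 (duration independent of onset) | 60 | 0.0% |
| 0.5 | 60 | 11.2% |
| 0.5 | 30 | 38.7% |
| 1 (late onset shortens sleep in full) | 60 | 38.5% |
| 1 | 30 | 58.8% |
| 1 | 0 (wake time fixed) | 69.0% |

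In the last row the SD of the daily totals equals the SD of the onsets, so nothing is lost. All rows treat dark-quiet-still time as an error-free measure of sleep duration.

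**4. Is another feature specified?** Data Analyses and Table 1 name none for number of awakenings, onset, offset or regularity of routine.

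**The case against.** The strongest reply is that the profile rule is not the whole of phase 1. The plan describes preprocessing more broadly, as deriving event features, and distinguishes continuous from intermittent streams. It treats nightly hours of sleep as a day-level measure of its own, so some sleep processing lies outside the level profiles. Table 1 also gives Sleep the unlock and screen events, call and message logs, app use and location, and gives Activities location. Detailed data reach the server. The list of weekly statistics is open-ended, and time-series analysis of shifts is planned.

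All of this stands, and it rules out a stronger reading. A reader might infer that sleep continuity, sleep timing and routine cannot be computed at all in this study, or that these constructs have no usable predictor. The documents do not support that: other collected streams could supply them, and day-to-day variation in the profiles does carry consistency in amounts of activity. What the reply does not provide is a feature. Hours of sleep is a duration, and the reference to events names none that measures continuity or timing.

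A second reply is that Aim 3 predicts weekly questionnaires, not awakenings or onset times. The sleep instruments are described as covering duration and quality, and a physical activity questionnaire suits time-at-level totals well. This also stands. A reader might infer that the sleep and activity models will be weak, but nothing in the documents or in the calculations above links the lost content to questionnaire performance.

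A third reply is that near-zero information on onset irregularity is only one extreme. The last table confirms this.

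**Conclusion.** The concern holds in a limited form. The profiles described for light, sound and accelerometer, and by the general rule for other fast-updating measures, do not change when time within the day is reordered. Sleep continuity, sleep and wake timing, and within-day routine cannot be recovered from them, and the plan specifies no other feature for these constructs. That conclusion is logical and does not depend on the simulations.

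The size does depend on assumptions. For onset irregularity, daily totals carry from about 0% of the variance to about 69%, the same as the seven onset times, with about 39% at half coupling and 30-minute noise. For awakenings, a single quiet-time total carries about 1% to 18% under the stated assumptions, without any contribution from unlock or screen events.

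Prediction of the questionnaires remains possible but may miss this content, and Aim 4 inherits whatever Aim 3 selects. Because the detailed data are kept on the server, the loss is reversible. Severity is moderate.

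**What to change.** In phase 1, before weekly aggregation:

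- Keep time-of-day bins (hourly or finer, on a noon-to-noon day so that a night is not split) for the light, sound, motion, location and screen streams.
- For each night, derive onset, offset, the longest dark-quiet-still run and the number of breaks in it.
- For each week, derive the variability of onset and offset, and the day-to-day agreement of location and activity by hour.
- Add these to the existing time-at-level totals as candidate features, and state for each which streams and time resolution it uses.

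The bin width and the noon-to-noon day are one workable choice; what matters is that order and clock time survive the first reduction. Defining the features in advance also avoids choosing them after the models have been seen.

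The cost is more feature-derivation code, a few sentences in Data Analyses, and a few more candidate features entering the planned PCA and FDR reduction. No new data collection is needed.
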